Adaptation for 2-1-1 Delivery and Feasibility/Acceptability Study (IRB #86129 & #92840). With scalability in mind, we next obtained funding from NCI to adapt the intervention for telephone delivery with 2-1-1 callers. Given successful history with 2-1-1 in our smoke-free home research which involved telephone delivery and mailed materials, we partnered with United Way of Greater Atlanta 2-1-1 for this adaptation pilot study from 2016 to 2018. We formed a Steering Committee to help adapt the intervention for urban households living in disadvantaged neighborhoods within the metro area.

In this recently completed one-arm study, we learned that telephone delivery is feasible, with comparable results in terms of changes in the home food environment and changes in the expected direction for eating and weight-related outcomes. Atlanta 2-1-1 introduced the study to callers and conducted a brief eligibility screener. If callers were interested in learning more, 2-1-1 line agents took their contact information and provided names and contact information to the EPRC via a secure website. Over a 3 month period, they provided 265 names. EPRC staff then screened, consented, enrolled, and collected baseline data on 101 of the 2-1-1 callers. Eligibility criteria were broad to make it easy for 2-1-1 to identify interested callers and because of the focus on healthy eating and weight gain prevention which applies to almost everyone. Core components of the HH/HF intervention remained the same as in the larger trial, but delivery took place over three months instead of five, and was reduced to six phone calls (no home visits) delivered at two week intervals over three months, with text messages tailored to barriers mentioned on the calls delivered on the off-

Table 2. HH/HF RCT Results for Home Food Environment Outcomes

Home Food Environment Outcome	Change from BL to Six Month F-UP	Intent to treat analyses (Baseline to 12 Month F-UP)+
Unhealthy drinks in the home	X	X
Unhealthy snacks in the home	X	X
Frequency of fruit shopping	-	X
Frequency of vegetable shopping	-	X
Family eating in front of TV	X	X
Healthy food preparation	X	X
Healthy food serving practices	X	X
Family meals from non-home sources	X	X
Family support for healthy eating	X	-
Telling others your weight	-	-

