x-SIGNIFICANT CHANGE IN DESIRED DIRECTION at $p<.05$. p-values for change between two time points results from independent t-tests and regression analyses; p-values for the ITT analysis are from growth modeling and refer to the significance of the interaction term of group and time

weeks. We did not include the physical activity actions given null results in both the earlier pilot and the main trial.

The majority of participants were African American (82%) and female (74%), with more men participating than expected. Close to half of the participants were unemployed (48%), and just 14% were college graduates with 10% not finishing high school. All participants reported annual household incomes < \$25,000. Typical household size was 2.8 members, and less than half had children in the household (45%). The mean age was 44, and 44% received SNAP benefits. Of the 101 completing baseline data collection, 75% completed the first coaching call, and 51% completed at least four of the six calls. Sixty percent were reached for follow-up one month post-intervention. Outcome measures consisted of the home environment survey used in our prior studies and two 24 hour dietary recalls at baseline and four months. Although not powered to detect change, we observed a significant increase in HEI scores^{14,57} (from 54.5 to 58.9), decreases in Kcal of 203 per day from pre to post, and decreases in self-reported weight of 4 pounds. Consistent with one or both prior evaluations of the HH/HF intervention, we documented significant changes in household food inventories, food shopping behavior, food preparation, family meals from non-home sources (e.g., not eating out or getting take out), and less eating with the TV on. Moderator analyses did not justify targeting the intervention to a specific subpopulation of callers. These results, which documented the feasibility of partnering with 2-1-1 to identify low-income individuals interested in a healthy eating/weight gain prevention intervention, combined with the potential reach of 2-1-1, position us for the current research project.

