To answer our effectiveness and implementation research questions, we will conduct an RCT with follow-up at four months and nine months post-baseline. The four-month post-baseline follow-up will document short-term outcomes and process data such as acceptability of the intervention. The nine-month post-baseline follow-up will assess maintenance of home food environment and dietary changes. Participants will be recruited by United Way of Greater Atlanta 2-1-1 and United Way of SWGA. EPRC staff will obtain informed consent and enroll participants and collect data at baseline and follow-up. Horizons Community Solutions staff will deliver the intervention to participants recruited from outside the Atlanta area and EPRC staff will deliver the intervention to callers from the Atlanta area.

Data Collection Procedures. The telephone interviews will be conducted by trained Emory research staff and graduate research assistants. All data collectors will be blind to group assignment and have no interactions with any intervention delivery related tasks, including mailings. At follow-up, if data collectors are unable to reach participants with the established telephone-based collection protocol, data collectors will text and email participants a unique survey link designed using REDCap for them to complete their home environment survey. A final attempt to collect data will be made via mail. Participants will receive a paper copy of the home environment survey asking them to complete it and mail it back.

Data collectors will be responsible for confirming eligibility of all interested participants referred by 2-1-1 and conducting informed consent to participate in the study. Once verbal informed consent has been documented, the baseline interview will be conducted. Two unscheduled dietary recalls will follow to ensure completion of a weekend and weekday recall for each participant. Similar procedures will be executed for follow-up data collection #1 and #2. Please see table below for data collection and payment schedules.

	Recruitment & Screening	Informed consent	Interview 1 Home Environment Survey	Interview 2 Dietary Recall 1	Interview 3 Dietary Recall 2
Baseline	X	X	\$40		
			X	X	X
Follow-up 1 (4-months post-baseline)			\$20	\$20	
			X	X	X
Follow-up 2 (9-months post-baseline)			\$20	\$20	
			X	X	X

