key aspects of motivational interviewing, such as reflective listening and rolling with resistance.^{64,65} Immediately after a participant completes baseline data collection, we will generate the home environment profile via a secure web-based application and send it along with the other intervention materials (i.e., family contract, healthy action checklist and stickers). The home environment profile presents tailored baseline data in a user-friendly format that helps participants identify aspects of their home environment that facilitate or hinder eating healthy. Tailoring is based on the household food inventory, frequency of grocery shopping for fruits and vegetables, frequency of purchasing fast food/restaurant food for family meals, food preparation and serving practices, eating in front of the TV, and weight monitoring.

The intervention will be delivered over 12 weeks with weekly contact alternating between phone and text/e-mail contact (see Table 3). The Coach will contact the participant one week after baseline data collection to review

the home environment profile and select the first healthy action. On the first call, the Coach will review the profile, then present a list of low-cost “healthy actions” that target possible environmental changes to make in the home. Using a series of open-ended questions, the coach guides the participant to select a healthy action to work on. This will be followed at weekly intervals by text/e-mail check-ins to reinforce progress and problem-solve challenges. Additional healthy actions are added in future calls, for a total of three healthy actions across three months. The participant will document the selected healthy actions on a family contract with stickers and their signature. The coaching calls, text messages and intervention materials are designed to increase behavioral capability, self-efficacy and behavioral intention to improve the home food environment for healthy eating and weight gain prevention. Participants will receive three seasonings, one portion size plate, and a magnetic grocery list pad after completing their 3rd coaching call.

Control Condition. Participants in the control condition will receive two mailings on healthy eating, the first from the *Dietary Guidelines For Americans*

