To assess the effectiveness of the HH/HF in the 2-1-1 population we will conduct traditional RCT analyses, using both complete case and intent-to-treat data (all participants). We will first assess statistical significance of change between baseline and each follow-up points with appropriate bivariate tests (e.g., independent t-tests, Wilcoxon-Mann-Whitney tests, chi-square tests of independence). We will use growth modeling as the intent-to-treat analysis as it allows for modeling of all available data without the need for multiple imputations based on the assumption of data missing at random.^{71,72} Hence, we will include any variables identified as being related to missingness into these models as covariate. We will utilize multiple imputation if there are issues with missing data for individual covariates.⁷³ In general, growth models will include time (calculated as time elapsed between the measurement point and baseline date) and an interaction effect between time and group assignment. We will assess the intraclass correlation (ICC) due to clustering in 2-1-1 call centers, but based on our previous research, ICCs are expected to be very small (< 1%) and we therefore do not anticipate the need to adjust for clustering. However, if the need arises, we will adjust for clustering using three-level modeling with Bayesian estimators due to the small number of clusters.

Furthermore, we will test differences in intervention effectiveness, i.e., conduct moderator analyses, for demographics/household characteristics, and baseline BMI using growth modeling with interaction effects between group assignment and the moderators of interest. Finally, we will use Structural Equation Modeling to assess changes to the home food environment as mediators as indicated in Figure 4. Data cleaning and analyses will be conducted using SAS 9.4 and Mplus 8.

We will also use the addresses of HH/HF study participants to investigate the relationship between food desert residence and primary and secondary outcome variables such as diet quality and household food inventories. To do so, participants' addresses will be geocoded using ArcGIS 10.8.2 and assigned to 2010 census tract data. These data will then be joined with USDA's Food Access Research Atlas dataset, which includes census tract-level information on food access. Using participant's census tract as an objective indicator of food access de-identifies participants' home locations.

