Data Analysis Plan for the assessment of implementation study (aim 2)

Descriptive analyses will be run on survey and coaching log/web analytic data to characterize the process measures and program implementation. Regarding data from 2-1-1 and Horizons leaders and staff, we will conduct analyses pooled across sites and by individual sites (i.e., the four 2-1-1s and Horizons versus EPRC) to understand variations in promotion, recruitment, and implementation. We will also develop a codebook based on evaluation questions and emergent themes from the transcripts. Two analysts will double code each transcript and resolve discrepancies through discussion. NVivo will be used for qualitative data analysis and management. We will then generate code reports using NVivo to facilitate identification of themes and develop matrices to aid in identifying themes and patterns across key categories such as type of 2-1-1 organization (e.g., Atlanta versus Macon/Columbus versus Albany), which differ in terms of staffing structure and organizational and community context. A similar approach will be taken for the analysis of qualitative data from intervention arm participants. The process evaluation data from program participants will be triangulated with the staff interviews to assess multiple stakeholders' perspectives.

Data Analysis Plan for the cost-effectiveness analysis (aim 3)

We will conduct a cost analysis and a cost-effectiveness analysis of the intervention, focusing on effects associated with improvements in diet (i.e., fruit and vegetable consumption, fewer empty calories) and avoidance of weight gain (relative to controls). The analysis will be conducted from the societal perspective and assume a lifetime horizon. We will use estimates of effectiveness of the intervention based on the analysis described above. In the baseline analysis, we will assume that behaviors persist for participants remaining lifetime. We will test the sensitivity of results to reasonable assumptions about effect durability, but most studies linking dietary behaviors to health outcomes in the literature focus on binary classifications of behaviors rather than exposure time. We will build a model that tracks participants from the beginning of the intervention to death. The analysis will conform to Panel on Cost-Effectiveness in Health and Medicine standards for conducting cost-effectiveness analyses.⁶⁸

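### Read naturally, the intent-to-treat growth model for HEI has one time-by-group slope, which ties the 4-month difference to 4/9 of the 9-month difference

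*Combined protocol and SAP*

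**What the plan says.** HEI is the primary outcome, measured at baseline, 4 and 9 months (Baseline and Follow-up Outcome Measures). The Data Analysis Plan for the hybrid-effectiveness implementation trial makes growth modeling the intent-to-treat analysis, on all available data under missing at random. The terms it names, in general, are time, calculated as "time elapsed between the measurement point and baseline date) and an interaction effect between time and group assignment". It names no visit, curved or piecewise term.

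The earlier trial has a one-term precedent. The footnote to Table 2 says "p-values for the ITT analysis are from growth modeling and refer to the significance of the interaction term of group and time".

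The design has distinct phases. Under Intervention Condition: "The intervention will be delivered over 12 weeks with weekly contact alternating between phone and text/e-mail contact". Under Field Methods for the trial: "The four-month post-baseline follow-up will document short-term outcomes and process data such as acceptability of the intervention", and then "The nine-month post-baseline follow-up will assess maintenance of home food environment and dietary changes".

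The Data Analysis Plan also has tests outside the growth model: "We will first assess statistical significance of change between baseline and each follow-up points with appropriate bivariate tests".

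**The concern.** A single slope on elapsed time assumes that the arm difference in change from baseline grows in proportion to time, up to the last visit. Coaching ends before the 4-month visit, and the two follow-up visits have different jobs: one records the short-term effect, the other asks whether it is kept. A gain that is then held, or partly lost, is not a line through zero.

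With one slope, the model has no separate parameter for the 4-month difference, so it cannot show how much of that difference remains at 9 months. This matters because it is the analysis meant to use all randomized participants, for the primary outcome.

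**Working it through.** The documents give no alpha, power, HEI standard deviation or HEI effect size for this trial, so there is no plan figure to reproduce. The check asks what a single slope estimates.

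**Inputs from the documents.** Visits at 0, 4 and 9 months (Field Methods). Enrolment of 800 (Recruitment) in balanced blocks (Randomization), read as 400 per arm. Feasibility study: 60% reached at follow-up, so 40% lost. Earlier trial, energy intake: -274 - (-69) = -205 kcal at 6 months and -195 - (-76) = -119 kcal at 12 months; 119/205 = 0.58.

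**Assumptions.** HEI SD 12; 4-month difference d = 2.5 points; equal correlation 0.4 between visits; 20% lost, contributing baseline only; two-sided 0.05. The share of the effect kept at 9 months, r, is not known for HEI.

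**Step 1: what the slope estimates.** Project the true arm differences (0, d, r·d) onto the model by generalized least squares: slope = last element of (X'WX)⁻¹X'Wδ. Here δ is the vector of differences, W is the information matrix for the three visits, and X holds time alone (only the named terms: common baseline) or a constant and time (group main effect added: free baselines). The weights on the three visits, scaled to slope × 9, are:

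- common baseline: -0.437, +0.168, +0.925
- free baselines: -0.983, -0.030, +1.013

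Fully sustained effect (r = 1):

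- common: slope × 9 = (0.168 + 0.925)d = 1.09d; slope × 4 = 4/9 of that = 0.49d
- free: slope × 9 = (-0.030 + 1.013)d = 0.98d; slope × 4 = 0.44d

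Across correlation 0.3 to 0.6 and loss of 20% to 40%, slope × 4 at r = 1 runs from 0.464d to 0.498d (common) and from 0.433d to 0.452d (free). These fractions do not depend on d or the SD.

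**Step 2: when the bias vanishes or reverses.**

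- Straight-line growth (0, 1.11, 2.5): slope × 4 = 1.11, which is exact.
- Delayed effect (0, 0.8, 2.5), common: 0.168 × 0.8 + 0.925 × 2.5 = 2.447, times 4/9 = 1.088.
- Delayed effect, free: -0.030 × 0.8 + 1.013 × 2.5 = 2.509, times 4/9 = 1.115. Both exceed the true 0.8.

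So the 4-month difference is understated when it is more than 4/9 of the 9-month difference, and overstated when it is less.

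**Step 3: power (%) under the assumptions above.** The joint test is the 2-df group-by-visit test.

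| Pattern | Baselines | Slope | Average of 4 and 9 months | Joint | 9 months |
|---|---|---|---|---|---|
| r = 1 | common | 89 | 95 | 90 | 82 |
| r = 1 | free | 69 | 83 | 74 | 70 |
| r = 0.8 | common | 75 | 90 | 84 | 63 |
| r = 0.8 | free | 49 | 74 | 66 | 51 |
| r = 0.58 | common | 54 | 81 | 77 | 39 |
| r = 0.58 | free | 28 | 63 | 60 | 30 |
| straight line to 2.5 | common | 83 | 74 | 75 | 82 |
| straight line to 2.5 | free | 70 | 55 | 60 | 70 |

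With 40% lost, slope v average is 79 v 87 (common) and 61 v 75 (free) at r = 1, and 43 v 69 and 26 v 55 at r = 0.58.

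**The case against.** The strongest reply is that the plan does not fix the model criticised here. It never says the time effect is linear, and its hedge leaves room for other terms. A reader might infer that the sponsor has committed to a straight line; the text does not support that. What stands is that the named terms and the earlier trial's practice both point to one slope, and that the time function for the primary outcome is left open.

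A reader might also infer that the short-term effect goes untested. It does not: the bivariate tests compare the arms at each follow-up. But they sit outside the missing-at-random intent-to-treat model and, as ordinarily run, use only participants with both measurements.

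Nor should fading be assumed. The Efficacy Trial section calls the HEI improvements sustained, and the longitudinal results were significant for HEI (p = .02) and for energy (p = .03), the outcome that supplies the 0.58. Such a test can therefore succeed, although that does not make it an estimate of the 4-month effect. With a larger assumed effect (d = 3.5, r = 1), slope v average is 99% v 100% (common) or 93% v 98% (free).

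Two further arguments are tempting but weak. The columns of Table 2 disagree for 3 of 10 outcomes. "Family support for healthy eating" was significant only at six months, but fruit and vegetable shopping were significant only in the growth model, and the time windows differ, so the table does not show that a slope misses effects. The cost-effectiveness plan says "In the baseline analysis, we will assume that behaviors persist for participants remaining lifetime", but that is a modelling assumption with planned sensitivity analyses, not evidence on the shape between 0 and 9 months.

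**Conclusion.** The point holds as a mismatch between the natural reading of the model and the design, and it should be fixed. If the HEI effect is sustained or fades, a single slope understates the 4-month difference. It returns about 0.44 to 0.49 of it when the effect is fully sustained, at assumed correlation 0.4 and 20% loss, and it cannot show retention. It would be wrong to conclude that the model always understates: there is no bias under straight-line growth, and the bias reverses if the effect is delayed.

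The power argument is secondary and rests on assumed SD, effect, correlation and loss. Against the two-visit average, the loss is 6 points (common baseline) or 14 points (free baselines) if the effect is sustained. It reaches 27 or 35 points at r = 0.58, which is an energy figure from an intervention with home visits and other follow-up times. Confidence is medium, because the documents leave the time function open.

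**What to change.** In the intent-to-treat model, code time as categorical visit (baseline, 4, 9 months) with group-by-visit terms. Fit it by likelihood to all available data under the same missing-at-random assumption. Adding a slope change at 4 months is an alternative: with three scheduled visits it has the same mean structure, and it keeps elapsed time. State whether baseline means are constrained equal. Report the 4-month and 9-month HEI differences from that one model, and label the bivariate and complete-case tests as supportive.

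The cost is SAP wording and a few lines of code, with no new data. There are three downsides:

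- Categorical visits need visit windows.
- If the effect truly grows in a straight line, the average contrast has less power than the slope (74% v 83% common, 55% v 70% free), and so does the joint test (about 75% and 60%).
- If 9 months is made primary with a common baseline, power is 7 to 15 points below the slope (82% v 89% at r = 1, 39% v 54% at r = 0.58), in exchange for an unbiased 9-month estimate. With free baselines it is about unchanged.

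Which visit or contrast is primary is a separate gap. It exists however time is coded.

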Flyer/Web method: Participating 2-1-1 agencies will have the option of creating a study information flyer for distribution (in-person or on their website). Content of this flyer includes information on study involvement, length, compensation, eligibility criteria, and study PI. Callers will have several different options (phone, text, or web link) to be connected to their local agency for preliminary screening.

We expect that 80% of callers will be eligible and based on our feasibility study, 50% will be reachable and interested in the research. We anticipate approximately 1700 callers will be referred to enroll **800** participants. Emory research staff will contact callers to describe the research activities in more detail, confirm eligibility, obtain verbal consent, and enroll them in the study. Participants will provide contact information for themselves and a person who can always locate them to aid in retention, and complete the baseline survey on the call. Following the completion of the baseline survey, we will call them two more times, to complete two dietary recalls. That will conclude their requirements for enrollment into the study. Both 2-1-1 and Emory versions of the eligibility screeners are included for review.

Recruitment for the assessment of implementation study (aim 2).

2-1-1 and Horizons leaders and staff and intervention arm participants will be selected for semi-structured interviews.

The following protocol will be used to recruit 2-1-1 and Horizons leaders and staff:

1. An introductory email notification and up to five reminders will be sent to selected 2-1-1 and Horizons leaders/staff inviting them to participate in interviews. Potential participants will be identified by the Directors overseeing the centers and/or have a study-related role. The email invitation will include a description of the study, study procedures, compensation for completing the semi-structured interview, etc. An opt-out option with instructions will be provided in the email notification and no further contact will be made with those who remove themselves from further participation.

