Participants will be randomized within site (i.e., Atlanta, Albany, Macon, Columbus) using a random number generator with balanced blocks of 10. To accommodate rolling enrollment, the lead statistician or Associate Director of Research Projects will receive participant IDs in meaningful time intervals (e.g., weekly) and communicate their group assignment to the intervention Coordinator.

Intervention Condition

The intervention is designed to target home-based environmental determinants of dietary behaviors (Figure 4). The intervention is grounded in empirical research showing associations between environmental factors and behaviors. The

intervention is also informed by Social Cognitive Theory and the Social Ecological Framework,^{17,59} both of which posit reciprocal influences between individuals and their environment.

Intervention strategies are also informed by coaching, goal-setting theory, and motivational interviewing.⁶⁰⁻⁶³ Our coaching approach is adapted from

Figure 4. Conceptual Model of Healthy Homes/Healthy Families Intervention

[figure not shown]

Table 3. Intervention Delivery Schedule

Timing by Week	Type of Contact	Description
0	Recruitment, consent, baseline data collection	Home environment profile generated and mailed, with other intervention materials (family contract, healthy actions, stickers)
1	Call	Coach call to review profile and select healthy action 1
2	Text/email message	Reinforce actions with tips
3	Call	Reinforce progress/problem-solve challenges
4	Text/email message	Reinforce actions with tips
5	Call	Coach call to select healthy action 2
6	Text/email message	Reinforce actions with tips
7	Call	Reinforce progress/problem-solve challenges
8	Text/email message	Reinforce actions with tips
9	Call	Coach call to select healthy action 3
10	Text/email message	Reinforce actions with tips
11	Call	Reinforce progress /problem-solve challenges
12	Text/email message	Reinforce actions with tips

Heimendinger's 5-stage model (discover, connect, create, design, activate).⁶⁰ Additionally, the coaches will use Version #7

Version Date: 1/24/24

[figure not shown]

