Participant surveys, completed one month after the intervention will include a number of process evaluation questions. We will ask about receipt of mailed materials, usefulness and relevance of materials, and satisfaction with the coaching calls. Coaches will also complete coaching logs to document goals set and barriers faced or anticipated. Semi-structured interviews will be conducted with four staff at each 2-1-1 (e.g., United Way Director, 2-1-1 director, line agent/resource manager and line agent/community connections specialist) (n=16) and with the Horizons coach and supervisory staff (n=2) via telephone or Zoom. Semi-structured interviews will also be conducted with intervention arm participants based on each of the eight healthy actions (n=45) and based on participants' food security status (n=35) via telephone or Zoom for a total of 80 interviews. Semi-structured interview guides for 2-1-1 and Horizons leaders and staff will cover topics to adoption, adaptation, acceptability, relevance, and maintenance. Semi-structured interview guides with intervention arm participants will cover topics related to barriers and facilitators to healthy action progress and maintenance, barriers and facilitators to healthy food access and healthy eating, and suggestions for program changes or improvements. Interviews will be recorded and transcribed verbatim. All interviews will be conducted by personnel not directly involved in other aspects of the study, to minimize social desirability bias. All study procedures, including the interviews, will occur by telephone. 2-1-1 and Horizons leaders and staff who complete the semi-structured interview will receive a \$40 gift card in appreciation of their time. Intervention arm participants who complete the semi-structured interview will also receive a \$40 e-gift card and/or mailed gift card.

Field Methods for cost-effectiveness study (aim 3)

We will collect program delivery tracking logs, partners' estimated time and costs as part of the cost-effectiveness analysis. We will also include data on call attempts for recruitment, program delivery, frequency and outcome of call contacts, etc. Participant surveys, completed one-month post intervention implementation, will include a number of process evaluation questions that will be used to assess implementation (from aim 1). These data sources will be used for the purposes of program document review to answer evaluation questions.

INFORMED CONSENT PROCESS

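### Clustering is checked by call center, within which participants are randomised, while variation between coaches, who exist only in the intervention arm, is not modelled and may leave the HEI interval too narrow

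*Combined protocol and SAP*

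**What the plan says.** The section Randomization states: "Participants will be randomized within site (i.e., Atlanta, Albany, Macon, Columbus) using a random number generator with balanced blocks of 10". The unit of randomisation is the individual and the site is the stratum.

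Under Field Methods for the hybrid-effectiveness implementation trial, delivery is divided by area: "Horizons Community Solutions staff will deliver the intervention to participants recruited from outside the Atlanta area", and the Emory center's own staff cover Atlanta. Under Intervention Condition (Table 3), each intervention participant has six individual coach calls over 12 weeks, alternating with text or e-mail messages. Under Control Condition, controls get two mailings and have no coach.

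On clustering, the Data Analysis Plan for the trial says "We will assess the intraclass correlation (ICC) due to clustering in 2-1-1 call centers" and continues: "ICCs are expected to be very small (< 1%) and we therefore do not anticipate the need to adjust for clustering". The fallback is this: "if the need arises, we will adjust for clustering using three-level modeling with Bayesian estimators due to the small number of clusters". The main model is described as follows: "growth models will include time (calculated as time elapsed between the measurement point and baseline date) and an interaction effect between time and group assignment". Variables found to predict missingness are added as covariates. Neither coach nor site is named as a model term. A comparison of Horizons with the Emory center appears only in the aim 2 implementation analysis.

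**The concern.** A call-center effect shifts intervention and control participants of the same site together, and the balanced blocks keep the arms nearly equal within site, so it largely cancels from the arm difference. A coach effect cannot cancel, because there is nothing on the control side to set against it. Participants of the same coach may share part of their outcome, through that coach's skill or style, and the number of independent observations in the intervention arm is then smaller than the number of participants.

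The plan therefore examines the level that does little harm and, from a small expected ICC there, concludes that clustering needs no adjustment. The expected value below 1% is stated in connection with call centers and does not carry over to coaches. At stake are the width of the interval and the p-value for HEI, the primary outcome. The effectiveness estimates also feed the cost-effectiveness model in aim 3.

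**Working it through.** **Inputs from the documents**
- Planned enrolment: "callers will be referred to enroll 800 participants". Balanced blocks, read as 1:1, give 800 / 2 = 400 per arm.
- Retention in earlier work (Relevant Prior Work): 60% in the one-arm 2-1-1 study, and 76.8% at 12 months in the earlier randomised trial. Applied to 400, these give 240 and about 307 analysed per arm.
- Expected site shares (recruitment section): about 40% Atlanta and 60% elsewhere.

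**Assumed, because the documents do not state them**
- Number of coaches: 5, 10 or 20 with equal caseloads.
- Coach ICC: 0.005 to 0.02.
- A two-sided 5% test.

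The plan gives no power calculation or coach figure that could be reproduced first.

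**Formulas.** With caseloads m, the intervention-arm design effect is DE = 1 + ICC × (Σm² / Σm − 1), where Σm² / Σm is simply m if caseloads are equal. In the control arm DE = 1. At 1:1, true SE / naive SE = √((DE + 1) / 2). The actual type I error is 2 × (1 − Φ(1.96 / ratio)).

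**Worked example.** Five coaches with 80 participants each, ICC 0.02: DE = 1 + 0.02 × 79 = 2.58; ratio = √(3.58 / 2) = 1.34; type I error = 14.3%.

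**Mildest corner.** Twenty coaches with 12 analysed participants each (240 per arm), ICC 0.005: DE = 1 + 0.005 × 11 = 1.055; ratio = √(2.055 / 2) = 1.014; type I error = 5.3%.

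**Type I error, equal caseloads**

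| Coaches | Analysed per arm | ICC 0.005 | ICC 0.01 | ICC 0.02 |
|---|---|---|---|---|
| 5 | 400 | 7.3% | 9.7% | 14.3% |
| 5 | 240 | 6.4% | 7.8% | 10.6% |
| 10 | 400 | 6.1% | 7.3% | 9.6% |
| 10 | 240 | 5.7% | 6.3% | 7.7% |
| 20 | 400 | 5.5% | 6.1% | 7.2% |
| 20 | 240 | 5.3% | 5.6% | 6.3% |

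With 307 analysed, the results lie between these; five coaches at ICC 0.02 give 12.2%.

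**One large caseload, as a possibility only.** Suppose one coach has 60% of the arm and four have 10% each.
- With 400 analysed: Σm² / Σm = (240² + 4 × 40²) / 400 = 160. At ICC 0.005, DE = 1.795 and the error is 9.7%. At 0.01, DE = 2.59, the ratio is 1.34 and the error is 14.3%.
- With 240 analysed: (144² + 4 × 24²) / 240 = 96. The error is 7.8% at ICC 0.005 and 10.7% at 0.01.

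**Does the call-center level matter?** This was checked by simulation: 6,000 runs, 800 participants, four sites at 40/20/20/20%, 1:1 within site, two-arm test without / with site terms.
- Call-center clustering only: 4.6% / 4.6% at site ICC 0.01, and 4.8% / 5.2% at 0.05. There is no inflation.
- Site ICC 0.01 with three Atlanta and three outside coaches: 10.1% / 10.2% at coach ICC 0.01, and 13.8% / 13.8% at 0.02. For six equal coaches the formula gives 8.9% and 12.8%, so the approximation is about one percentage point low here.
- Five plus five coaches: 6.7% / 6.9% at coach ICC 0.01, and 10.1% / 10.3% at 0.02. The formula gives 7.3% and 9.6%.

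Site terms do not remove the coach effect.

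**The case against.** Several objections have force.

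- **No coach variation is documented.** A reader might infer that the standard error is too small as a matter of fact. The documents do not show that. If the coach ICC is zero, the test keeps its 5% level.
- **It depends on the target of inference.** If coaching has no effect with any coach, coaching creates no coach variance and the naive test is valid. Inflation needs coaches who truly differ around an average of zero, treated as a sample from a wider pool. Inference limited to the coaches used is defensible, and the plan does not say which is meant. The concern is conditional on this choice.
- **The caseload may be modest.** A reader might also infer from the aim 2 phrase "with the Horizons coach and supervisory staff (n=2" that a single coach carries all participants outside Atlanta, about 60% of the arm. That phrase describes whom to interview, not how many coaches are employed. The section on training of the study team speaks of intervention staff at both organisations and of newly hired coaches.
- **Standardisation may keep the ICC low.** Coaches have a two-day training, recorded sessions with feedback, and boosters, and the home profile is generated by an application. In the 2-1-1 pilot only 75% completed the first coaching call, and those never coached can hardly share a coach effect. This bears on which ICC is plausible, but the plan does not measure it.
- **The arithmetic is not the planned model.** The growth model tests a group-by-time term, so the relevant quantity is coach variance in change. The percentages illustrate size and do not predict it.

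None of this shows that the call-center check or its fallback would detect a coach effect confined to one arm.

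**Conclusion.** The point holds in conditional form. The call-center check addresses a level that does not inflate the error of the arm comparison, and no planned outcome model captures variation between coaches. The HEI interval may therefore be too narrow if outcomes differ between coaches and inference is meant to go beyond the coaches used.

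The size cannot be settled from the documents. Over the assumed range, the true standard error is about 1% to 34% larger than the naive one and the type I error is about 5.3% to 14.3%: close to nominal with many coaches and a low ICC, material with few coaches. If one coach had 60% of the arm, it would be about 8% to 14% at ICC 0.005 to 0.01. All figures rest on assumed coach numbers and ICCs, 1:1 allocation, a two-sided 5% test and a two-sample approximation. The documents do not support saying that the planned p-value is wrong, or that such a concentrated caseload exists.

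**What to change.** 1. Include site, the randomisation stratum, as a fixed effect in the growth model in place of the call-center ICC check. This costs nothing. It reflects the design but does not deal with coach variation.
2. Record the coach ID for each intervention participant. Coaching logs and an electronic delivery application are already planned, so this should need little extra work.
3. Pre-specify a partially nested sensitivity model for HEI: a coach random effect on change in the intervention arm only, with small-sample degrees of freedom. Report the coach ICC and the resulting interval beside the main result. Say whether inference is meant for the coaches used or for a wider pool.
4. State that if one coach covers a whole area, the coach effect and an area-specific intervention effect cannot be separated, and that the model does not solve this.

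The cost is one additional model, and multilevel modelling is already foreseen with SAS and Mplus. The downside is that with few coaches the variance component is imprecise and the interval may widen.
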